5.3 Data entry and modification

Data entry and modification: The data of CRF were input by the independent double-entry method. Data managers check the data in the case report form and find out that questions are asked by clinical inspector. Data managers modify and confirm the data according to the researchers' answers, and if necessary, a clinical inspector can issue the questionnaires again.

After data entry and inspection, data managers, main researchers, bidders and statistic analysts jointly audit the data, and complete the final definition and judgment of the analysis population.

5.4 Data summary and report

The principal investigator writes a clinical investigation summary report in accordance to CONSORT guidelines and archives the data. Any changes to the original statistical plan should be stated and justified in the CIP and/or in the final report.

CHAPTER 6: SAFETY REPORTING AND MEDICAL MANAGEMENT

6.1 Adverse events

6.1.1 Definition

6.1.1.1 Adverse event (AE)

An AE is any adverse medical event, unintended disease or injury, or any unfavorable clinical sign (including an abnormal laboratory finding) that occurs to the subject, user, or another person, whether or not related to the investigational device. This includes events related to:

All events related to the investigation or control device.

All events related to the investigation process (all processes in the CIP).

Note: For users or others, the AEs here are limited to all of those related to the investigational device.

6.1.1.2 Adverse device effect (ADE)

Adverse events related to use of investigational medical device:

Include AEs caused by inadequate or inappropriate descriptions of usage, deployment, implantation, installation, operation, or any fault of the investigational medical device.

Include AEs caused by use error or deliberate misuse of the investigational medical device.

6.1.1.3 Adverse event severity determination

Observe the procedure, severity, actions taken and outcome of AEs and fill them in the adverse event report form. According to the following criteria, the severity of AEs can be classified into mild, moderate, and severe.

Mild: Transient or mild discomfort that does not affect daily life and action; no special measures or medical intervention/therapy required.

Moderate: Mild effect on daily life and activity; take measures or medical intervention/therapy if necessary.

Severe: Serious effect on daily life and activity; special measures or medical intervention/therapy required; hospitalization if necessary.

6.1.2 Recording

All AEs reported by the patients or discovered from Electronic Medical Record were assessed for severity and relationship with study treatment by the investigators, with appropriate measures taken in time and detailedly documented.

6.2 Serious adverse events

6.2.1 Definition

SAEs can be defined as any events leading to death or serious deterioration of health during clinical trials, including:

Fatal disease or injury;

Leading to permanent defect of body structure or function;

Requires hospitalization;

Medical or surgical intervention is needed to avoid permanent defects in body structure or function.

6.2.2 Measurements and reporting

Table List of contact information for SAE reporting

Contacts	phone or fax
Changhai Hospital	[contact]
Shanghai Municipal Food and Drug Administration	[contact]
State Food and Drug Administration	[contact]

When SAE occur in our clinical trials, the researchers should immediately take appropriate treatment measures for the subjects, and report in writing to the management department of clinical trials of medical devices in the clinical trial institutions under their jurisdiction and notify the applicants.

SAEs had to be reported the principal investigator and to DSMC, ethics committee and the local provincial food and drug administration within 24 hours. For death events, the investigation sites and investigator should provide the ethics committee and sponsor with all information they need.

6.3 Unexpected adverse device events (UDAE)

Unexpected adverse device events refer to serious adverse health or safety effects, life-threatening problems or deaths caused by or associated with devices that are unaware of their nature, severity or frequency in research programs, instructions for use and instructions for clinical trials, or any other serious unexpected problems related to ncMCE.

6.4 Relationship determination

The reporting investigator will complete the SAE report in the CRFs, including date of event, admissions, diagnosis details, date of discharge, whether result in the experiment and its sequela. Researchers should give targeted treatment and follow-up to AEs until symptoms disappear or remain stable.

Any adverse event should be judged on the basis according to the following criteria:

Irrelevant: There was no correlation between AE and the use of ncMCE .

possibly irrelevant: The occurrence of AE is more likely to be related to other factors, such as combination of drugs or accompanying diseases, or the occurrence time of AE indicates that it is unlikely to have a causal relationship with ncMCE .

Possibly relevant: AE may be caused by the use of ncMCE . There is a reasonable time sequence for the occurrence of incidents and the use of research-related devices and can exclude the effect of concomitant treatment and combined medication.

Affirmative relevant: The type of adverse event has been identified as a side effect of ncMCE and cannot be explained by other reasons. The occurrence order of the event strongly suggests causality.

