6.5 Device deficiency

Device deficiency refers to deficiency of a medical device in identification, quality, durability, reliability, safety or performance. Medical device deficiencies include malfunction, misuse or use error and inadequate labeling.

The investigator shall record the discovered device deficiencies during the clinical investigation and analyze the cause of the event together with the sponsor, form a written analysis report, and propose a suggestion on continuation, suspension or termination of the investigation, which will be reported by the medical device clinical investigation management department to the Ethics Committee for review.

Both investigators and subjects can make a complaint against the treatment product and control product at any phase of the clinical study.

CHAPTER 7: MISCELLANEOUS CONSIDERATIONS

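### Do causality grades that name only ncMCE bias the safety comparison against the new system?

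*Combined protocol and SAP*

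**What the plan says.** Section 6.4 opens its scale to all events: "Any adverse event should be judged on the basis according to the following criteria". It sets no limit by arm. The four grades then refer to ncMCE. The lowest is "Irrelevant: There was no correlation between AE and the use of ncMCE", the third begins "Possibly relevant: AE may be caused by the use of ncMCE", and the highest requires that "The type of adverse event has been identified as a side effect of ncMCE and cannot be explained by other reasons". Within the third grade, the timing criterion is broader: "There is a reasonable time sequence for the occurrence of incidents and the use of research-related devices". Section 6.3 has a similar mix, speaking of devices in general and ending with "or any other serious unexpected problems related to ncMCE".

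Other sections cover both arms. The adverse event definition in 6.1.1.1 includes "All events related to the investigation or control device". Section 6.1.2 asks investigators to assess each event's relation to the study treatment, without naming an arm. Section 6.5 says "Both investigators and subjects can make a complaint against the treatment product and control product at any phase of the clinical study".

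On use of the data, 4.3.1 makes the occurrence of adverse events a primary endpoint, covering any event up to two weeks after the procedure. Chapter 8 plans 40 patients in two groups with no sample size calculation, and describes no table or test of related events.

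Section 2.9, on benefits and risks, refers to 107 subjects, a placebo arm, improvement in FC-related symptoms and a vibration risk. It does not mention SARS-CoV-2 infection.

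**The concern.** According to 4.1 and Appendix 1, ncMCE is the MCE system with a remote workstation and an audio-visual link added, and both arms use an endoscopic capsule. Abdominal pain or capsule retention can be due to the capsule in either arm. If relatedness means relatedness to ncMCE, an investigator could reason that a control patient never received ncMCE and grade the event as unrelated. The same event in the ncMCE arm would be graded as related.

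The trial is open-label, and 5.2 describes blinding only for the assessment of completion, so the grader may know the arm. Section 6.1.2 requires every event to be graded, so the grades will exist. If they were tabulated by arm, two equally safe procedures could look different, with ncMCE appearing worse.

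Section 2.9 adds to the unease. Its subject count, comparator, benefit and vibration risk do not match the trial described in 2.2, 3.1, 4.1 and Chapter 8, which suggests text carried over from another study.

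**Working it through.** The plan gives no figure to reproduce: it states no sample size calculation and no adverse event rate. The check has two parts.

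**1. Does the text force a zero count of related events in the MCE arm?**

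- The first three grades name ncMCE, and read strictly they point that way.
- The highest grade asks whether the *type* of event is a known side effect of ncMCE, whether other causes are excluded, and whether the order of events suggests causality. It does not require that this patient received ncMCE. Since both arms use the capsule, retention in an MCE patient could meet it as written.
- The timing criterion in the third grade refers to research-related devices, which includes the MCE equipment.
- 6.1.1.1, 6.1.2 and 6.5 are neutral between arms or name the control device.
- 6.1.1.2 defines adverse device effects by the investigational device, which may explain the wording of 6.4.

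A zero count is therefore one possible reading, and the text does not force it.

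**2. How large could the distortion be?**

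Inputs: 40 patients allocated 1:1 (3.1, Chapter 8), so 40/2 = 20 per arm; two-sided P < 0.05 (Chapter 8). Assumed: the same true proportion *p* of patients with a related event in both arms, and a Fisher test comparing related events by arm. The plan specifies neither.

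With *x* related in one arm and 0 in the other, the two-sided Fisher P is 2·C(20,x)/C(40,x):

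- x = 4: 2 × 4,845 / 91,390 = 0.106
- x = 5: 2 × 15,504 / 658,008 = 0.047

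Five against none is thus the smallest such split that reaches P < 0.05. With X ~ Bin(20, p) for ncMCE, the three scenarios are:

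- *Literal*: every related MCE event is graded unrelated. Chance of a false P < 0.05 = Pr(X ≥ 5).
- *Half mis-graded*: Y ~ Bin(20, p/2) for MCE; sum the joint probabilities over all pairs with Fisher P < 0.05.
- *Even-handed*: Y ~ Bin(20, p); same sum.

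| Assumed p | Expected counts, literal (20p v 0) | Literal | Half mis-graded | Even-handed |
|---|---|---|---|---|
| 5% | 1 v 0 | 0.26% | 0.16% | 0.19% |
| 10% | 2 v 0 | 4.3% | 1.7% | 1.2% |
| 20% | 4 v 0 | 37% | 7% | 2.3% |

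At 5%, half mis-grading gives a slightly lower figure than even-handed grading, so there is no inflation. The large figure appears only when a high event rate and complete mis-grading are combined.

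**3. Which planned outputs use the grades?**

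- Primary safety endpoint (4.3.1): any event in patients, related or not.
- Secondary endpoints (4.3.2): none concerns relatedness.
- SAE reporting within 24 hours (6.2.2): triggered by seriousness alone.
- Chapter 8: no analysis of related events.
- 6.1.1.1 does limit adverse events in users and other persons to those related to the investigational device. That rule does not reach patients, and 4.3.1 provides separately for monitoring the endoscopist for infection.

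**4. Section 2.9.** No calculation uses 107; 3.1 and Chapter 8 both give 40. The comparator is MCE in 3.1, 4.1 and Appendix 1. Infection is followed up under 4.3.1 and 5.2 although 2.9 omits it.

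**The case for a change.** The strongest case for a change is that safety is half of the primary endpoint, grading is compulsory, the grader may know the arm, and the operative scale names one arm only. Neutral wording elsewhere does not repair that scale. It shows that two readings exist, so the grade may depend on who applies it. The correction would be a few words, with no new data and no change to the endpoint.

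Much of this is right. The inconsistency is real, a control-arm capsule event might be graded unevenly, and any error would run against ncMCE. What does not carry over is the consequence. Harm needs a grader who follows the letter of 6.4 against the rest of Chapter 6, and also a by-arm summary of related events that the plan does not call for. A significance statement would need an unplanned test as well.

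Nor is a change free. Under 2.8 it requires ethics committee approval, and re-grading events already judged in an open-label trial would itself be judgement after the fact. Knowledge of the arm adds little here, because an ncMCE-only rule would mislead a blinded grader too.

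**Conclusion.** No change to the plan follows, because none of its planned results would improve. Section 6.4 is loosely worded. An investigator who reads it with 6.1.1.1 and 6.1.2 would grade each event against the capsule procedure the patient received, and the text allows this. The patient-level primary safety count, the secondary endpoints and SAE reporting are the same under either reading.

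Any distortion is confined to a descriptive split of related events that the plan does not specify. Its size is unknown because the documents give no event rates. Under the assumptions above, the chance of a false P < 0.05 with complete mis-grading is 0.3% at a 5% rate (0.2% if graded evenly), 4.3% at 10% (1.2%) and 37% at 20% (2.3%). The last figure should not be quoted without its three conditions: a 20% related-event rate, every related MCE event mis-graded, and an unplanned Fisher test.

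The mismatches in 2.9 are a separate clerical matter. That section does not describe this trial and disagrees with 2.2, 3.1, 4.1, 4.3.1 and Chapter 8, but no analysis draws on it. This conclusion would need to be revisited only if a by-arm comparison of related events became a reported result.

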4.2 Study intervention

- Patients were required to report personal history and have chest computed tomography or nucleic acid testing to exclude COVID-19 infection within 3 days before their examination. Patients who are confirmed to have a COVID-19 infection and symptoms of pneumonia should be treated at special medical institutions first. Only when this population needs immediate endoscopy should those procedures be done in specific wards that have COVID-19 infection prevention protocols in place [13]. On arrival at the hospital in the morning after an overnight fast (> 8 hours), each patient took a 400-mg simethicone suspension dissolved in 100 mL water 40 minutes before they ingested the capsule ingestion according to standardized gastric preparation [14]. Another 800 to 1000 mL of water could be taken 10 minutes before capsule ingestion to distend the stomach [12]. Then, a patient's hands were disinfected and they were given the data recorder after entering the examination room. Next, a patient laid down on the examination bed next to the computer workstation, assumed the supine or left-lateral decubitus position, and swallowed the capsule, which had already been activated. An endoscopist controlled capsule movement with the help of a magnet robot using two joysticks in front of the workstation or automatically using a default mode. To ensure that the gastric mucosa was completely visualized, the endoscopist directed a patient to change position to supine and right-lateral decubitus. In the ncMCE group, a patient and the endoscopist entered two rooms through different routes and gastric preparation was under the remote guidance [15]. The audio-visual exchange system provided a platform for the endoscopist to see and communicate with a patient during examination. The data recorder was embedded in the examination bed to avoid cross-infection of COVID-19 among patients and simplify the disinfection process. Enhanced personal protective equipment (PPE) including an N95 mask, isolation gown with water resistance, head cover, eye protection, and face shield [11] should be worn by medical staff in the capsule endoscopy examination room when performing MCE. The steps for donning and doffing PPE were strictly followed, according to the standard process [16]. Medical masks were used as basic PPE for endoscopists in the ncMCE group (Supplementary material, Table 1) [17]. After each examination, the returned data recorder was disinfected using ultraviolet light, 75% alcohol, or ethylene oxide and the sheets on the bed were replaced.

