
4.3 Study outcomes

4.3.1 Primary efficacy outcome

The primary endpoints were feasibility assessed by completion rate (CR) and safety evaluated by the occurrence of AE. CR was defined as complete observation of the cardia, fundus, body, angulus, antrum, and pylorus of the stomach with no technical failure. Technical failure included incomplete observation, direct contact in the ncMCE group, and examination discontinuation. The safety of ncMCE was evaluated 2 weeks after the procedure for any AEs, such as infection with SARS-CoV-2 and capsule-related AEs including abdominal pain, nausea, vomiting, and capsule impaction or retention. In the current study, the endoscopist was continuously monitored for infection until 2 weeks after the last examination.

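### The causality scale in Section 6.4 has no grade for a well-timed event whose other possible cause is neither excluded nor more likely, and the gap leans towards 'not related' (minor)

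*Combined protocol and SAP*

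**What the plan says.** Section 6.4 requires every AE to be placed on a four-step scale.

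- *Irrelevant*: nothing links the event to the device.
- *Possibly irrelevant* has two routes. One reads: "The occurrence of AE is more likely to be related to other factors, such as combination of drugs or accompanying diseases". The other is timing that makes a causal link unlikely.
- *Possibly relevant*: ncMCE may be the cause, the time sequence is reasonable, and the investigator "can exclude the effect of concomitant treatment and combined medication".
- *Affirmative relevant*: a recognised side effect of ncMCE, with timing that strongly suggests causality, which "cannot be explained by other reasons".

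Section 4.2 describes the gastric preparation: "each patient took a 400-mg simethicone suspension dissolved in 100 mL water 40 minutes before they ingested the capsule". It also permits a water load: "Another 800 to 1000 mL of water could be taken 10 minutes before capsule ingestion to distend the stomach".

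Section 4.3.1 makes the occurrence of AEs a primary endpoint. Among the AEs to look for it names "capsule-related AEs including abdominal pain, nausea, vomiting, and capsule impaction or retention". Section 6.1.1.1 defines an AE regardless of its relation to the device and includes events arising from any process in the plan. Section 6.1.1.2 defines adverse device effects as AEs related to use of the device. Under Section 6.1.2 the investigators assess relationship.

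**The concern.** A grade worded as 'possibly' related would normally admit events for which the device is one plausible cause among others. Here it demands that concomitant treatment and medication be ruled out first. The grade above it is at least as demanding, so both related grades depend on eliminating alternatives.

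The trial's procedures make this more than a drafting curiosity. All patients take a drug preparation within the hour before the capsule, and many may also drink a large volume of water. Upper gastrointestinal symptoms that day are the ones Section 4.3.1 calls capsule-related, and the preparation is an obvious candidate for an alternative cause. If investigators read the rule literally, such symptoms could be kept out of the related grades by its wording and not by a judgement about the device. The trial is open-label, and the plan describes no independent adjudication of relatedness, so nothing else in it would correct the lean.

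**Working it through.** The plan gives no figure to reproduce: Chapter 8 states that no sample size was calculated, and no AE rate is assumed anywhere. The check is therefore mainly one of logic.

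**Step 1. Run one event through the scale.** Take an event with plausible timing, for which another cause is possible, cannot be excluded, and is not more likely than the capsule examination.

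| Grade (Section 6.4) | Requirement | Met? |
|---|---|---|
| Irrelevant | No correlation with ncMCE | No: timing is plausible and a link is possible |
| Possibly irrelevant | Other factors more likely, or timing unfavourable | No: neither applies |
| Possibly relevant | Reasonable timing, and concomitant treatment and medication excluded | No, if the other cause is a treatment or medication: not excluded |
| Affirmative relevant | Known side effect, no other explanation | No: another explanation exists |

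The event has no grade, yet one must be assigned. The two related grades require the alternative to be eliminated, so the wording pushes a literal reader towards the unrelated side.

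**Step 2. Can such an event occur here?** Section 4.2 gives simethicone to each patient, in both arms, 40 minutes before the capsule. The extra water is worded as optional. Section 4.3.1 lists nausea, vomiting and abdominal pain among the events of interest. Section 4.2 sits under the study intervention and Section 6.1.1.1 counts every process in the plan, which suggests that the preparation belongs to the examination. Section 6.4 refers to concomitant treatment and combined medication without saying that the preparation falls outside them. The classification is open, so the case can arise.

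**Step 3. What depends on the grade?** The primary safety endpoint is the occurrence of AEs, and Section 6.1.1.1 counts them whether or not related. An ungraded or down-graded symptom stays in that count. The capsule-related label in Section 4.3.1 and the adverse device effects in Section 6.1.1.2 do depend on relatedness.

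**Step 4. Illustration with assumed rates.** Forty patients at 1:1 give 40/2 = 20 per arm. Let p be the true rate per patient of examination-related symptoms on the day, and k the share that passes the exclusion test. Both are assumptions; the documents give neither. The chance that at least one event in an arm is graded as related is 1 − (1 − pk)^20.

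| p | k = 1 | k = 0.5 | k = 0.1 | k = 0 |
|---|---|---|---|---|
| 5% | 64.2% | 39.7% | 9.5% | 0% |
| 10% | 87.8% | 64.2% | 18.2% | 0% |
| 20% | 98.8% | 87.8% | 33.2% | 0% |

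For example, with p = 10% and k = 0.5: 1 − 0.95^20 = 64.2%. The result depends heavily on k, which the wording of Section 6.4 leaves open. Likewise, 0 of 20 related events gives a one-sided 95% upper bound of 1 − 0.05^(1/20) = 13.9%, but that bound means something only if related events can in fact be graded as related.

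**The case against.** A reader might infer that examination-day symptoms can hardly ever be graded as related, and that a report of no related AEs would simply follow from the rule. The documents do not support that, for four reasons.

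- No section classes the preparation as concomitant treatment or combined medication. Section 4.2 presents it as part of the study procedure, and the examples of other factors in Section 6.4 are drugs in combination and accompanying disease.
- The criterion asks for an *effect* to be excluded, not for nothing else to have been taken. Onset and course may allow this, as with pain that begins at swallowing or during magnetic steering.
- Only simethicone is stated for every patient. The large water load "Another 800 to 1000 mL of water could be taken 10 minutes before capsule ingestion", and nothing calls water a treatment.
- A figure of about zero related events arises only by setting k = 0, which assumes the conclusion.

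A reader might also infer that the primary safety endpoint is distorted. It is not: it counts any AE, and Chapter 8 plans no analysis by relatedness. Capsule impaction or retention and SARS-CoV-2 infection are not plausibly confounded by the preparation, and simethicone is common to both arms.

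All of this stands, and it limits how far the problem reaches. It does not close the gap in Step 1, which exists however the preparation is classified, since any other treatment or medication could produce it. Nor does it settle how the preparation should be treated in grading.

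**Conclusion.** The point holds as a minor fault in a stated rule. Section 6.4 leaves a class of events without a grade and leans towards 'not related'. Examination-day nausea, vomiting and abdominal pain can fall into that class, because the status of the preparation is undefined. The labels exposed are capsule-related AEs (Section 4.3.1) and adverse device effects (Section 6.1.1.2); the overall AE count is untouched.

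The size cannot be determined from the documents. The table in the working spans the possibilities under assumed rates of 5% to 20% and any pass share from none to all; it is not an estimate. The conclusion rests on reading the criteria of Section 6.4 as written, and on investigators not having a grading instruction outside these documents.

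**What to change.** Reword 'possibly relevant' in Section 6.4 so that it applies when the time sequence is reasonable and a contribution of the capsule examination, including its preparation, cannot be ruled out, even if another treatment, medication or disease may also have contributed. Keep 'possibly irrelevant' for implausible timing or a clearly more likely other cause. This closes the gap and settles how the preparation is treated in causality grading.

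The text change is one sentence. AEs already graded would need to be looked at again, as far as the AE forms hold enough detail on onset and course; the documents do not show that they do. The downside is that a few more AEs will be listed as related. The overall AE count by arm stays the same.
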